Accumulating evidence shows that the HER family displays a high degree of plasticity and the multiple members provide compensatory signaling leading to acquired resistance in response to therapeutic intervention to a single target (7,8). Simultaneous targeting of more than one HER family receptor is frequently able to reverse the resistance to the initial drug and is often more efficacious than single-receptor targeting alone (9,10,11). Inhibiting more than one HER family member may thus be critical to limiting acquired resistance and more effectively treating cancer.

In addition, the cells within a tumor may display extensive heterogeneity and therefore do not respond equally to individual therapies. This intra-tumor heterogeneity comprises not only clinically important traits such as ability to metastasize and resist therapy, but these cells may also express biomarkers suggesting potential alternative therapeutic targets, including the members of the HER family (12,13).

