5.3.1 Screening

When the trial site identifies a patient suitable for screening, the Sponsor or designee should be contacted to ensure that a cohort is open for inclusion. Once confirmed, the patient may be approached for informed consent. Screening activities may begin only once written informed consent has been obtained.

All patients giving informed consent to participate in the trial will receive a unique patient number. This number is composed of a five-digit prefix (which identifies the country and site), and a three-digit number, allocated sequentially starting from 001 for the first patient screened at the site, 002 for the second patient screened, etc.

The trial site staff must complete a Screening and Allocation Form, stating the allocated patient number along with the planned dates of screening and first scheduled Pan-HER administration (Cycle 1/Day 1, in the following C1/D1). The planned date of C1/D1 will need to be agreed upon in collaboration with the Sponsor or designee for the dose-escalation cohorts in order to ensure adequate time between dosing of the first patient and dosing of any subsequent patients within each cohort. The completed Screening and Allocation Form will then be sent to the Sponsor or designee prior to or on the day of Screening.

All screening activities must be performed within 14 days prior to C1/D1, unless otherwise specified. Individual screening assessments may be repeated prior to C1/D1, if justified and documented by the Investigator.

Once eligibility has been confirmed in accordance with the inclusion and exclusion criteria (Sections 6.1 and 6.2, respectively), the Screening and Allocation Form will be fully completed and signed by the Investigator and resent to the Sponsor or designee. Sponsor or designee will approve each patient for start of treatment. A copy of the fully executed Screening and Allocation Form will be returned to the trial site for archiving. This form documents the allocated dose and schedule of Pan-HER.

Furthermore, once eligibility is confirmed:

- All patients in Part 1 and 2 will have a blood sample taken for exploratory biomarker analysis
- All patients in Part 1 and 2 will have a skin biopsy performed
- Patients included in Part 1 of the trial and consenting to the optional tumor biopsy procedure
 will have a tumor biopsy performed, unless it is confirmed that suitable archival tissue is
 available for central analysis.

Confidential Page 40 of 156

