6.1 Inclusion Criteria

For inclusion in the trial, all of the following criteria must be fulfilled:

- 1. Written informed consent given before any trial-specific procedure is initiated
- 2. Male or female, at least 18 years of age at the time of informed consent
- 3. Eastern Cooperative Oncology Group (ECOG) performance status (PS) of 0 or 1
- 4. Life expectancy >3 months assessed during Screening
- 5. Documented (histologically- or cytologically-proven) epithelial tumor malignancy that is locally advanced or metastatic, having received all therapy known to confer clinical benefit
- 6. If female and of childbearing potential, a negative pregnancy test
 - Note: Women are considered of childbearing potential unless they have been hysterectomized, have undergone tubal ligation or have been postmenopausal for at least one year.
- 7. Not of childbearing potential or agrees to use a medically effective method of contraception as per institutional standards during the trial and for 3 months after the last dose of trial drug

Note: Women are considered of childbearing potential unless they have been hysterectomized, have undergone tubal ligation or have been postmenopausal for at least one year.

8. Part 2 ONLY:

a. Epithelial malignancy (HER2+ solid tumor malignancy Basket Cohort, pancreatic carcinoma, and 2 other tumor types to be specified in a protocol amendment), measurable according to RECIST v1.1 that has been confirmed by CT or MRI within 4 weeks prior to C1/D1

Note: Measurable disease is defined as 1 or more target lesions assessed by CT or MRI. A tumor lesion situated in a previously irradiated area is considered measurable only if subsequent disease progression has been documented in the lesion

b. Willingness to undergo a pre-and post-dosing biopsy (total of 2 biopsies) from primary or metastatic tumor site(s) considered safe for biopsy

Note: For patients on anticoagulant therapy at the time of biopsy, it must be deemed safe by the Investigator to have anticoagulant therapy held prior to the procedure

Confidential Page 48 of 156

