8.7 Tumor Biopsy (Central Laboratory)

Part 1: Optional (requires separate informed consent) and only applicable for patients where a tumor lesion is considered safe for biopsy. To be performed after eligibility has been confirmed.

Part 2: Required. Patients must have tumor lesion considered safe for biopsy. To be performed after eligibility has been confirmed.

• Screening, after confirmation of eligibility

Note: Archival tissue may be accepted, if suitable for central analysis as specified in the laboratory manual. It must be ensured that the archived biopsy can be made available to the central laboratory prior to deciding to omit the tumor biopsy procedure at time of screening.

• End of Cycle 2 (prior to dosing Cycle 3) or upon PD, whichever occurs first

Note: End of cycle assessments may be conducted at any time during the week prior to Day 1 of the next cycle. If feasible, it is preferred that the second biopsy is taken from the same tumor site from which the first biopsy was taken.

To include a tumor biopsy performed by a core biopsy of a locally recurrent or metastatic lesion. The procedure at time of screening will take place after eligibility has been confirmed and prior

Confidential Page 82 of 156

to first Pan-HER administration. The tumor biopsy must be performed with minimal morbidity to the patient by a percutaneous core needle biopsy either with or without the aid of an imaging modality chosen at the discretion of the physician performing the biopsy.

Biopsy specimens will be obtained using standard sterile surgical techniques and formalin-fixed, paraffin-embedded according to standard laboratory practice. All tumor tissue samples should be reviewed by a pathologist to confirm the presence of tumor cells before the tissue sample (block or slides) is sent to the central laboratory for analysis. A detailed laboratory manual specifying sample collection, handling, storage, and shipment will be provided to the trial sites.

Analysis of tumor biopsies will include target engagement (EGFR, HER2 and HER3) and may furthermore include proteins and genes that are unknown or have not been included in the scientific hypotheses at the present time of trial, but that, during the collection of data from this trial, may evolve as new candidate genes and markers related to Pan-HER safety, efficacy, or mechanism of action.

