4.2 General Presentation Considerations

Baseline

‘Baseline’ is defined as the last available pre-treatment assessment, considering both scheduled and unscheduled assessments.

Safety assessments at Cycle 1 Day 1 with no time of assessment (i.e. Vital Signs and Body Measurements, ECOG PS, Physical Examination) are assumed to be taken pre-treatment.

End of Treatment (EOT)

‘End of Treatment’ is defined as the first assessment on or after the last dose of study treatment, considering both scheduled and unscheduled assessments.

Unscheduled assessments

Unscheduled assessments will be presented in listings in chronological order.

Post Baseline unscheduled assessments (for Clinical Laboratory, ECG QTc, etc.) will be used for determination of worst result (i.e. Maximum and Minimum post Baseline result) as well as the maximal laboratory CTCAE grade if applicable; also, all post baseline tumor evaluation assessments will be used to derive BOR.

Except considered as Baseline, EOT or worst result, unscheduled assessments will not be included in summaries.

PAREXEL International
Statistical Analysis Plan Template for Early Phase Studies

Symphogen A/S
Sym013-01

Treatment Day

‘Treatment Day’ will be calculated relative to the date of C1/D1 as follow:

- assessments taken before the first infusion of IMP

Treatment Day = Assessment Date - First IMP infusion Date

- assessments after the first infusion of IMP

Treatment Day = Assessment Date - First IMP infusion Date + 1.

Missing Data

In case of partially missing date of birth or date of diagnosis, the following rule will be applied: if year and months are known but day is missing, then the day will be imputed as 15th; in case of only year known, the day and month will be imputed as 15th June.

Specific rules for handling for missing efficacy assessments are detailed in section 4.10.1.3.

Methods for handling missing concomitant medication and adverse events dates are detailed in sections 4.8 and 3.2.4.2 respectively.

Imputations will be used to derive parameters, in listings original data will be presented as collected.

Data Listing

All original and derived parameters for all consented patients will be listed.

All listings will include scheduled and unscheduled measurements.

Unless specified otherwise, data in listings will be presented by dose regimen (Q1W or Q2W), dose group, patient, and visit (ordered by date and time within patient).

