4.10.3.3 Tumor Biopsy

The date of the tumor biopsy, the tumor site, expression results of EGFR, HER2, and HER3 and Ki67 staining will be listed. EGFR, HER2 and HER3 receptor down modulation and changes in Ki67 in tumor biopsies (may not be available in Part 1), measured by percentage and nominal difference in target expression from baseline to end of Cycle 2 or PD (whichever comes first) in tumor biopsy samples will be presented by tumor type using descriptive statistics including scatter plots of values at end of Cycle 2 versus baseline.

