 - In the event of suspected PD, a CT/MRI is to be performed as soon as possible.
 - In the event of CR/PR, a confirmatory CT/MRI is to be performed 28 (+7) days after the first assessment of CR/PR.
- 12) A CT/MRI at EOT should only be performed if the previous CT/MRI has been performed > 3 weeks before; a CT/MRI scan at 1M FUP should only be performed if no CT/MRI documents disease progression before or at EOT.
- 13) Tumor marker evaluation to include tumor markers that are part of the trial site standard practices as indicated by humor type, if applicable.
- 14) Archival tumor tissue, applicable for patients in Part 1 only if tissue is available. To be assessed locally, preferably by immunohistochemistry (IHC). Does not need to be repeated if EGFR and HER2 status have been assessed previously and the pathology report is available to document findings.
- 15) Extended PK sampling for PK profiling will be done starting C1/D1 and C1/D2. Refer to [Table 11](#) for further details.
- 16) Skin biopsy: All patients enrolled will undergo skin biopsies. Sample is to be obtained during screening after patient eligibility has been confirmed. Sampling is to be repeated Cycle 1 Day 8 (prior to dosing) and Cycle 1 Day 15 (prior to dosing).
- 17) Tumor biopsy, **Optional for patients in Part 1.** Required for all patients in Part 2. To be assessed centrally. Tumor biopsy is to be performed after patient eligibility has been confirmed. Archival tissue may be accepted at screening if suitable for central analysis. Sampling is repeated at the end of Cycle 2 or upon PD, whichever occurs first. Refer to [Section 8.7](#) for further details.
- 18) Biomarker blood sample: To be obtained during screening after patient eligibility has been confirmed. Sampling is to be repeated at the end of Cycle 2 or upon PD, whichever occurs first, and at EOT.
- 19) Premedication: For Part 1, premedication is mandatory prior to each dose of Pan-HER. For Part 2, premedication is mandatory prior to each dose of Pan-HER during Cycle 1. In Part 2, premedication may be withdrawn after Cycle 2 on a patient-by-patient basis, if the patient is without evidence of IFRs. Refer to [Section 7.2.1](#) for details.

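### Archival tissue can serve as baseline for receptor change in tumor, and SAP 4.10.3.3 does not separate those pairs from pairs with a fresh screening biopsy

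*SAP*

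**What the plan says.** Part 1 tumor biopsies are optional. For patients who consent, Protocol 5.3.1 says they "will have a tumor biopsy performed, unless it is confirmed that suitable archival tissue is" available for central analysis. Protocol 8.7 adds the condition: "Archival tissue may be accepted, if suitable for central analysis as specified in the laboratory manual". Footnote 17 of the SAP's copy of the schedule keeps the allowance: "Archival tissue may be accepted at screening if suitable for central analysis".

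SAP 4.2 gives one baseline definition for all assessments. Baseline "is defined as the last available pre-treatment assessment, considering both scheduled and unscheduled assessments". It sets no time window and no rule on tissue source.

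SAP 4.10.3.3 then reports receptor down-modulation and Ki67 change, "measured by percentage and nominal difference in target expression from baseline to end of Cycle 2 or PD", by tumor type, with scatter plots against baseline. Biopsy date and tumor site are listed but play no part in the summary. Table 14.2.3.2 and Figures 14.2.4 to 14.2.7 carry the asterisk that puts them in the abbreviated study report.

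**The concern.** A change from baseline measures target engagement only if the baseline describes the tumor just before the first dose. An archival block may not. Under Protocol 6.1, patients enter "having received all therapy known to confer clinical benefit", and SAP 4.6 expects some to have had anti-EGFR or anti-HER2 drugs. If the block was taken before such treatment, the reported difference covers that treatment as well as Pan-HER.

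The protocol gives its own reason to expect movement. Section 3.1.2 says that "the HER family displays a high degree of plasticity" and describes compensatory signaling under single-target therapy. Loss of a receptor under earlier treatment would look like engagement by Pan-HER. Compensatory up-regulation would hide engagement. The block may also come from another lesion, whereas Protocol 8.7 says that "it is preferred that the second biopsy is taken from the same tumor site" as the first.

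Tumor target engagement is part of secondary objective 4. With optional biopsies there will probably be few pairs, so one or two archival baselines could shape a summary.

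**Working it through.** The plan gives no figure to reproduce. The check is a reading of the text, followed by arithmetic on assumed values.

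**Can archival tissue become the baseline?**
1. Protocol 5.3.1 does not call for a fresh biopsy where suitable archival tissue is confirmed.
2. SAP 4.2 takes the latest result before treatment. With both samples, the fresh biopsy is the baseline. With only the block, the block fits the definition.
3. SAP 4.10.3.3 has no split by tissue source and no sensitivity analysis.
4. Nothing states outright that archival results enter the calculation. SAP 3.2.2 lists archival tissue as its own variable. Table 14.2.3.2 is titled for tumor biopsy only, while Listing 16.2.6.5 combines archival tumor and tumor biopsy. The heading of SAP 4.10.3.1 includes archival tumor, but its text gives no rule for it.

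So the plan permits an archival baseline without stating one.

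**What would it do to the reported change?**
Let A be expression in the block, B the true level just before C1/D1, and C the level at end of Cycle 2. Let L be the fractional fall from A to B, and E the true fall on Pan-HER.

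- B = A × (1 − L) and C = B × (1 − E)
- Reported fall = 1 − C/A = 1 − (1 − L)(1 − E)
- Excess over the true fall = L × (1 − E)

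The documents give neither L nor E. All values below are assumed.

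| L (before Pan-HER) | E (on Pan-HER) | Reported fall |
|---|---|---|
| 10% | 0% | 10% |
| 20% | 0% | 20% |
| 40% | 0% | 40% |
| 20% | 30% | 1 − 0.80 × 0.70 = 44% |
| −20% (a rise) | 30% | 1 − 1.20 × 0.70 = 16% |

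The same in raw values, on an assumed 0–300 scale: A = 200, B = 120, C = 108. The reported change is (108 − 200)/200 = −46%. The change on Pan-HER is (108 − 120)/120 = −10%.

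**What would it do to a group mean?**
If a share s of pairs has an archival baseline with the same L and E, the mean is off by s × L × (1 − E). With L = ±20% and E = 30%, that is s × (±14) percentage points. The share s is not given and may lie anywhere from 0 to 1, so the error in this example runs from none to 14 points either way.

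**The case against.** The strongest case against is that the SAP may never have meant archival tissue to be a baseline. SAP 4.10.3.3 speaks of tumor biopsy samples, SAP 3.2.2 places the biopsy at screening after eligibility is confirmed, and archival tissue is a separate variable there. That separate entry may simply be the local assessment in Protocol 8.3.3. This has force, and it is why the point is put as a possibility. It does not settle the matter. Protocol 8.7 accepts the block in place of the screening biopsy, for an analysis that includes target engagement. SAP 3.2.2 also adds HER3 to the archival markers, while Protocol 8.3.3 covers only EGFR and HER2. That hints at central testing, though it is an inference.

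Other objections stand in part:

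- The laboratory manual may limit age or intervening therapy. It was not available, so the gap is shown only for the protocol and SAP.
- Biopsy dates, sites and prior anti-EGFR and anti-HER2 therapy are listed, so a reader could trace pairs by hand. The summary table and figures would still combine them.
- Dropping every archival pair would discard recent blocks with no therapy in between. Separate display avoids that.
- The same-site preference applies only where feasible, so fresh pairs may differ in site too. Site is a minor part of the point.

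A reader might infer that earlier treatment effects are in fact being reported as Pan-HER engagement. The documents do not support that, because the number of archival baselines is unknown. A reader might also infer a distorted dose choice for expansion. SAP sections 1 and 4.14 say that the trial stopped during Part 1 and that no patient entered Part 2.

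**Conclusion.** The concern holds in conditional form. The protocol lets suitable archival tissue replace the screening biopsy, the SAP's baseline rule would admit it when no fresh biopsy exists, and the change analysis does not tell the two apart. Expression changes before Pan-HER may therefore be mixed with its effect, in either direction.

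The size cannot be stated from the documents. The conclusion rests on three assumptions: that at least one analysed pair has only an archival baseline, that therapy or time between collection and C1/D1 altered expression, and that the laboratory manual does not already rule this out. SAP 4.10.1.2 describes all analyses as descriptive and exploratory, skin biopsies have no archival substitute, and no Part 2 dose rests on the result. What is at risk is the reading of Table 14.2.3.2 and Figures 14.2.4 to 14.2.7 in the study report. The change is cheap and should be made.

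**What to change.** In SAP 4.10.3.3, state whether archival tissue can be baseline. Then, for Table 14.2.3.2 and Figures 14.2.4 to 14.2.7:

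1. Base the main change-from-baseline summary on pairs whose baseline is a fresh screening biopsy.
2. Show archival-baseline pairs separately: a distinct symbol in the figures, and separate rows or a listing in place of pooled rows.
3. For each archival pair, give tissue date, site, and whether anticancer therapy was given between tissue collection and C1/D1, with anti-EGFR and anti-HER2 therapy marked.

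The flag in item 3 is a new derivation. SAP 4.6 identifies prior anti-EGFR and HER2 regimens but does not relate them to the tissue date. Treatment dates are collected under Protocol 8.1.5. Whether the block's own collection date is recorded should be confirmed.

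The cost is SAP wording, one derived variable and fewer pairs in the main summary. No new biopsy is needed.

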4.10.4 Pharmacokinetics

4.10.4.1 Pharmacokinetic Concentrations

Serum concentrations for each of the six monoclonal antibodies in Pan-HER will be listed by mAb, dose schedule, dose group, patient, actual time relative to dosing, scheduled time and time deviation from scheduled time. The unit for the concentrations will be $\mu\text{g/mL}$.

Patient profiles serum concentrations vs. time points for each mAb will be plotted by dose schedule and dose group.

The following definitions are used for PK plots and tables:

PAREXEL International
Statistical Analysis Plan Template for Early Phase Studies

Symphegen A/S

Sym013-01

- First profile for weekly: all PK points from Cycle 1 Day 1 to Cycle 1 Day 8 (pre-dose)
- 2nd profile for weekly (4th dose): all PK points from Cycle 1 Day 22 to Cycle 2 Day 1 (pre-dose)
- First profile for biweekly: all PK points from Cycle 1 Day 1 to Cycle 1 Day 15 (pre-dose)
- 2nd profile for biweekly (3rd dose): all PK points from Cycle 2 Days 1 to Cycle 2 Day-15 (pre-dose).
- Dosing/sampling occasions for weekly dosing: Week 1, 2, 3, 4, 5, 6 etc., EOT, 1MFUP
- Dosing/sampling occasions for biweekly dosing: Week 1, 3, 5, 7, 9 etc., EOT, 1MFUP
- Peaks: serum concentration for each mAb assessed at EOI for each dosing occasion
- Troughs: serum concentrations for each mAb assessed prior to SOI for each dosing occasion

Violations of scheduled sampling will be reviewed on a patient by patient basis by Symphegen and PAREXEL. Following data review by Symphegen's pharmacokinetic expert, data points may be excluded from mean calculations and parameter calculation based on the below criteria:

- Individual outlying data points which are markedly deviating from the preceding and following time points
- Data points or PK profiles which are not compatible with known physiological processes underlying the PK properties
- Unexpected events or protocol deviations documented in e.g. laboratory notes or in protocol deviation reviews

Exclusions will be documented in the study files and the PC/PP files.

Following plots will be produced:

PAREXEL International
Statistical Analysis Plan Template for Early Phase Studies

Symphogen A/S

Sym013-01

- One panel per mAb, Dose Schedule and Dose group combination showing a profile for each patient: Patient Profiles for concentration vs. Actual Time by Dose Schedule and Dose Group (peak and trough for each dosing occasion) – Linear
- One panel per mAb, Dose Schedule and Dose group combination showing a profile for each patient: Patient Profiles for concentration vs. Actual Time by Dose Schedule and Dose Group (peak and trough for each dosing occasion) Semi-log
- One panel per patient with overlaid profiles of all six mAbs: concentration of the six mAbs vs. Actual Time (peak and trough for each dosing occasion) – Semi-log
- One panel per mAb, Dose Schedule and Dose group combination showing a profile for each patient: Patient Profiles for concentration vs. actual time by Dose Schedule and Dose Group (First and 2nd profiles) – Linear
- One panel per mAb, Dose Schedule and Dose group combination showing a profile for each patient: Patient Profiles for concentration vs. actual time by Dose Schedule and Dose Group (First and 2nd profiles) – Semi-log
- One panel per patient with overlaid profiles of all six mAbs vs. actual time (First and 2nd profiles) – Semi-log

Above plots produced per mAb, Dose Schedule and Dose group combination will be composed by one panel for each mAb; moreover, each panel will be composed by the following 7 sub-panels

Sub-panel a) all patients in q1w - 1mg/kg

Sub-panel b) all patients in q1w - 2mg/kg

Sub-panel c) all patients in q1w - 4mg/kg

Sub-panel d) all patients in q1w - 6mg/kg + P

Sub-panel e) all patients in q2w - 6mg/kg

Sub-panel f) all patients in q2w - 9mg/kg and 9mg/kg + P

PAREXEL International
Statistical Analysis Plan Template for Early Phase Studies

Symphogen A/S

Sym013-01

Sub-panel g) all patients in q2w - 12mg/kg + P

Descriptive summary (n, arithmetic mean, SD, median, minimum, maximum, geometric means, and CV% values) of serum concentrations of each of the six mAbs will be tabulated by dose schedule, dose group and nominal sampling time. Following tables will be produced:

Summary of concentration for each of the six mAbs by Dose Group and Time Point (First and 2nd profiles)

Summary of concentration for each of the six mAbs by Dose Group and Time Point (Peak and trough for each dosing occasion)

The arithmetic and geometric means of the serum concentrations of each of the six mAbs vs. nominal time points will be plotted by dose group with +/-1 standard deviation (for arithmetic means). In figures of geometric means, error bars will be calculated using the following formula: $\text{Exp}(\text{mean_Ln} \pm \text{sd_Ln})$ where 'sd_Ln' denotes the standard deviation of the concentration values on the log base 10 scale and 'mean_Ln' denotes the arithmetic mean of the concentration values on the log base 10 scale.

The following mean concentration vs. time plots will be produced:

- Arithmetic Mean Concentration for each of the six mAbs vs. Planned Time Point by Dose Group and Dose Schedule (First and 2nd profiles) – Linear
- Geometric Mean Concentration for each of the six mAbs vs. Planned Time Point by Dose Group and Dose Schedule (First and 2nd profiles) – Semi-log
- Arithmetic Mean Peak and Trough Concentrations for each of the six mAbs vs. Planned Time Point by Dose Group and Dose Schedule (peaks and troughs at all dosing occasions) – Linear
- Geometric Mean Peak and Trough Concentrations for each of the six mAbs vs. Planned Time Point by Dose Group and Dose Schedule (peaks and troughs at all dosing occasions) – Semi-log

PAREXEL International
Statistical Analysis Plan Template for Early Phase Studies

Symphogen A/S
Sym013-01

